2.3 Treatment Assignment and Blinding

All subjects will be assigned a unique identification number by the IRT at the screening visit. For subjects who rescreen, the screening number assigned by the IRT at the initial screening visit should be used. The IRT will assign a randomization number that will encode the subject's treatment group assignment according to the randomization schedule.

Subjects who meet eligibility criteria at Baseline will be randomized in a 2:2:2:1:1 ratio to one of the five treatment groups:

- Group 1: upadacitinib 22 mg QD (N = 40) (Period 1) → upadacitinib 22 mg QD (Period 2)
- Group 2: upadacitinib 11 mg QD (N = 40) (Period 1) → upadacitinib 11mg QD (Period 2)

- Group 3: upadacitinib 6 mg QD (N = 40) (Period 1) → upadacitinib 6 mg QD (Period 2)
- Group 4: placebo (N = 20) (Period 1) → upadacitinib 22 mg QD (Period 2)
- Group 5: placebo (N = 20) (Period 1) → upadacitinib 11 mg QD (Period 2)

Randomization will be stratified by the age group (≤ 50 and > 50), Baseline disease severity (T-VASI < 15 and ≥ 15), and status of active vitiligo (Yes/No) defined as follows:

- Active: Showing new lesions or progression (enlargement) of existing lesions within the last 6 months and/or presenting clinical subtypes indicative of progressing vitiligo (i.e., confetti-like depigmentation, trichrome pattern, or Koebner phenomenon).

At Week 24, subjects who were randomized to placebo at Baseline will be switched to either 22 mg (Group 4) or 11 mg (Group 5) upadacitinib in a blinded fashion per pre-specified randomization assignments.

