2.4 Sample Size Determination

Assuming a Week 24 percent change from Baseline in F-VASI of 0% in the placebo arm, a conservative estimate based on a prior study in vitiligo,¹ the planned total sample size of 160 subjects (40 subjects in each upadacitinib group, 40 subjects in total in the placebo groups) will provide more than 90% power to detect the treatment difference of 40% reduction (assuming a standard deviation of 54.8%) in at least 1 upadacitinib group versus placebo using a 2-sided significance level of 0.1 based on the two-sample t-test.

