9.0 Efficacy Analyses

9.1 General Considerations

All efficacy analyses will be conducted in the ITT Population in each period (ITT_1 and ITT_2). All tests will be 2-sided at an alpha level of 0.1.

The Primary Analysis will be performed after all ongoing subjects have completed Week 24 or have prematurely discontinued prior to Week 24, data pertaining to Period 1 has been cleaned, and the database has been locked. This will be the only and final analysis for the efficacy endpoints in Period 1.

For analysis in Period 1, continuous endpoints and categorical endpoints will be analyzed using Mixed-Effect Model Repeat Measurement (MMRM) and Cochran-Mantel-Haenszel (CMH), respectively.

The analysis models and imputation methods for categorical and continuous endpoints in Period 1 and Period 2 are summarized in the following table:

Table 1. Analysis Models and Imputation Methods

Period	Type of Variables	Imputation Method	Intercurrent Events Handling	Analysis Model
Period 1	Continuous	MMRM ^a	The treatment policy strategy is used in this study. Under this strategy, all values for the variable of interest are used regardless of the intercurrent event.	MMRM model includes treatment, visit and treatment by visit interaction, stratification factors (age group [≤ 50 and > 50] ^e , baseline disease severity [T-VASI < 15 and ≥ 15] ^d , and status of active vitiligo [Yes/No]), and baseline measurement
	Categorical	NRI-MI ^b	The treatment policy strategy is used in this study. Under this strategy, all values for the variable of interest are used regardless of the intercurrent event.	CMH test adjusting for stratification factors (age group [≤ 50 and > 50], baseline disease severity [T-VASI < 15 and ≥ 15], and status of active vitiligo [Yes/No])
Period 2	Continuous	AO ^c	The treatment policy strategy is used in this study. Under this strategy, all values for the variable of interest are used regardless of the intercurrent event.	ANCOVA includes treatment, stratification factors (age group [≤ 50 and > 50], baseline disease severity [T-VASI < 15 and ≥ 15] ^d , and status of active vitiligo [Yes/No]), and baseline measurement
	Categorical	AO ^c	The treatment policy strategy is used in this study. Under this strategy, all values for the variable of interest are used regardless of the intercurrent event.	Descriptive summary

CMH = Cochran-Mantel-Haenszel; ANCOVA = Analysis of Covariance

- Mixed-Effect Model Repeat Measurement.

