Non-Responder Imputation while incorporating Multiple Imputation (MI), NRI-MI, will be the primary approach to handle missing data for categorical endpoints in Period 1 (Section [9.2](#) and [Appendix E](#)).

- If there are missing data due to COVID-19 or any other missing data that can be reasonably assumed to be Missing at Random, a total of 30 datasets will be generated by PROC MI, and subjects will be characterized as responders or non-responders based on MI imputed values.
 - If not all the imputed datasets are identical, analysis will be performed as described in [Appendix E](#).
 - If all the 30 imputed datasets are identical, all statistical inferences will be calculated using the first imputed dataset: 1) The corresponding 95% CIs will be constructed based on normal approximation to the binomial distribution. 2) Adjusted differences, 95% CIs and p-values for the comparisons between each upadacitinib group and placebo will be calculated based on CMH test adjusting for stratification factors.
- If there are no missing data due to COVID-19 or any other missing data that can be reasonably assumed to be Missing at Random, the NRI-MI method will be the same as traditional NRI method. All statistical inferences will be calculated using the NRI imputed datasets.

For long-term efficacy, descriptive summary statistics including frequencies and percentages for categorical endpoints, along with 95% CIs based on normal approximation, will be provided based on as observed data.

Unless otherwise specified, any subject who is randomized based on a wrong stratum will be analyzed according to the actual stratum the subject belongs to.

"Baseline" refers to the last non-missing observation before the first administration of study drug or randomization if no study drug is given.

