2.5.1 Analysis of Each Dataset

For each of the K 'complete' datasets, the CMH test will be used to estimate the treatment difference versus placebo and the corresponding standard error.

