  IF 0<=WK2<=0.5*BASE THEN VASI50_2=1;
  ELSE VASI50_2=0;
  IF 0<=WK4<=0.5*BASE THEN VASI50_4=1;
  ELSE VASI50_4=0;
  IF 0<=WK8<=0.5*BASE THEN VASI50_8=1;
  ELSE VASI50_8=0;
  IF 0<=WK12<=0.5*BASE THEN VASI50_12=1;
  ELSE VASI50_12=0;
  IF 0<=WK18<=0.5*BASE THEN VASI50_18=1;
  ELSE VASI50_18=0;
  IF 0<=WK24<=0.5*BASE THEN VASI50_24=1;
  ELSE VASI50_24=0;
RUN;
```

```
*****
*/
/*      DATA HANDLING STEPS TO MERGE COVID-19 or Other MAR STATUS OMITTED
*/
/*      PLACE TO ADD DATA HANDLING AND MERGING STEPS
*/
*****
*/
/*FOR MI, SKIP THE FOLLOWING CODE, PROCEED TO THE CODE AFTER ANALYSIS
MODEL *//*OVERRIDE MISSING VALUES NOT DUE TO COVID-19 or Other MAR WITH
TRADITIONAL NRI*/
DATA ALLF; SET ALL;
  /*COVID19 XX='Y' IF MISSING AT WEEK XX IS DUE TO COVID-19 or Other
MAR; IF NOT, OVERRIDE WITH TRADITIONAL NRI*/
  IF COVID19_2 NE 'Y' THEN VASI50_2=VASI50NRI_2;
  IF COVID19_4 NE 'Y' THEN VASI50_4=VASI50NRI_4;
  IF COVID19_8 NE 'Y' THEN VASI50_8=VASI50NRI_8;
  /*VARIABLE VASI50NRI_XX: TRADITIONAL NRI DATA AT WEEK XX, WHICH COVERS
THE SPECIAL HANDLING SUCH AS THE BEFORE-AND-AFTER EXCEPTION*/
  IF COVID19_12 NE 'Y' THEN VASI50_12=VASI50NRI_12;
  IF COVID19_18 NE 'Y' THEN VASI50_18=VASI50NRI_18;
  IF COVID19_24 NE 'Y' THEN VASI50_24=VASI50NRI_24;
RUN;
PROC SORT DATA=ALLF; BY _IMPUTATION_ SUBJID; RUN;

*****
/*ANALYSIS MODEL*/
*****

/*KEY CODE: ANALYZING EACH 'COMPLETE' DATASET*/
/*****
/*COMPARE TREATMENT GROUPS 1 (PLACEBO) AND 2 (HIGH-DOSE) ONLY*/
DATA ALL; SET ALL;
  WHERE TRT01PN IN (1,2);
RUN;

/*INDIVIDUAL-LEVEL DATA --> # OF RESPONDERS & # OF SUBJECTS, TO BE READ-
IN TO PROC STD RATE*/
PROC FREQ DATA=ALL;
  BY _IMPUTATION_;
  TABLES TRT01PN*AGEGR1N*TVAGR1N*ACTVGR1N*VASI50_24/LIST NOCUM NOPRINT
  OUT=COUNT_TABLE;
  /*WEEK 24 RESULTS AS AN EXAMPLE*/
RUN;
DATA COUNT_TABLE; SET COUNT_TABLE;
  DROP PERCENT;
```

```
RUN;
PROC TRANSPOSE DATA=COUNT_TABLE OUT=FREQ_TABLE PREFIX=RESP;
ID VASI50_24;
BY IMPUTATION_ TRT01PN AGEGR1N TVAGR1N ACTVGR1N;
VAR COUNT;
RUN;
DATA FREQ TABLE1; SET FREQ_TABLE;
CASE=RESP1;
SIZE=SUM(RESPO, RESP1);
KEEP _IMPUTATION_ TRT01PN AGEGR1N TVAGR1N ACTVGR1N CASE SIZE;
RUN;

/*RE-ORDER TO SET 1 (PLACEBO) AS THE REFERENCE GROUP*/
DATA FREQ_TABLE2; SET FREQ_TABLE1;
IF TRT01PN=2 THEN TRT01PN=0;
RUN;

/*CALCULATE THE COMMON RISK DIFF FOR EACH COMPLETE DATASET*/
PROC STDRATE DATA=FREQ_TABLE2
METHOD=MH STAT=RISK EFFECT=DIFF;
BY _IMPUTATION_;
POPULATION GROUP=TRT01PN EVENT=CASE TOTAL=SIZE;

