STRATA AGEGR1N TVAGR1N ACTVGR1N / ORDER=DATA STATS(CL=NONE) EFFECT;
ODS OUTPUT EFFECT=EFFECT;
RUN;

/*COMBINING RESULTS USING PROC MIANALYZE*/
*****
PROC MIANALYZE DATA=EFFECT;
ODS OUTPUT PARAMETERESTIMATES=RISK_DIFF_MH;
MODELEFFECTS RISKDIFF;
STDERR STDERR;
RUN;
```

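### When imputed datasets differ, the responder test becomes a pooled Wald test whose standard error, under the usual large-stratum variance, is about 10% too small for 8 strata and 40 per arm

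*SAP*

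**What the plan says.** SAP 9.1 sets the level for efficacy testing: "All tests will be 2-sided at an alpha level of 0.1". Responder endpoints in Period 1 are compared by a CMH test adjusted for age group, baseline T-VASI category and active vitiligo, with NRI-MI for missing data. The analysis then follows one of two routes.

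- **Nothing to pool.** If no values are handled by multiple imputation, the NRI data are analysed directly. If all 30 imputed datasets are identical, the first is used and, with the adjusted differences and intervals, "p-values for the comparisons between each upadacitinib group and placebo will be calculated based on CMH test adjusting for stratification factors".
- **Datasets differ.** Appendix E applies. Its section 2.5.1 says "the CMH test will be used to estimate the treatment difference versus placebo and the corresponding standard error". Section 2.5.2 pools these by Rubin's formula and bases tests and intervals on the pooled estimate divided by the root of its pooled variance, referred to a t distribution.

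The sample code in Appendix E 3.0 obtains the estimate and standard error from PROC STDRATE with "METHOD=MH STAT=RISK EFFECT=DIFF" and "STRATA AGEGR1N TVAGR1N ACTVGR1N / ORDER=DATA STATS(CL=NONE) EFFECT", which is 2 x 2 x 2 = 8 strata. Neither the text nor the code states a variance formula.

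**The concern.** On the second route the procedure is still called a CMH test, but the p-value comes from a Wald statistic on a stratified risk difference, so its validity depends on the standard error. A variance built from p(1-p)/n in each stratum-by-arm cell suits large strata. Here a cell holds about five subjects. In a cell of n subjects that form is too small by the factor (n-1)/n on average, and it is zero in a cell of one. The shortfall accumulates over strata and passes into the pooled variance.

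At stake are the p-values and 95% intervals for F-VASI 75, F-VASI 50 and T-VASI 50 at Week 24 and for the additional responder endpoints. They would look more certain than the data allow, and the error rate would depend on whether imputed response statuses happened to vary between datasets.

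**Working it through.** **Inputs from the documents.** Two-sided level 0.1 (SAP 9.1). Sample size: "40 subjects in each upadacitinib group, 40 subjects in total in the placebo groups" (SAP 2.4). Allocation: "randomized in a 2:2:2:1:1 ratio" (SAP 2.3), so each dose is 1:1 against pooled placebo. Eight strata (Appendix E 3.0). Thirty imputations (SAP 9.1). Placebo mean change 0% and SD 54.8% (SAP 2.4).

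**The plan's own figure.** For a 40-point difference the standardised effect is 40/(54.8 x sqrt(2/40)) = 3.26. Power at two-sided 0.1 is 94.7% (normal) or 94.4% (noncentral t), which agrees with the stated figure of more than 90%. It concerns the continuous primary endpoint and is unaffected. The plan gives no operating characteristics for the responder test beyond the nominal 0.1.

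**Assumption.** PROC STDRATE with the Mantel-Haenszel method uses the large-stratum variance

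V = sum of w_h^2 [p1h(1-p1h)/n1h + p0h(1-p0h)/n0h] / (sum of w_h)^2, with w_h = n1h n0h/(n1h + n0h).

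**Analytic bias.** Take n_h per arm in stratum h, n per arm in total, K informative strata (both arms represented) and a common rate p. Then w_h = n_h/2. The numerator of the true variance is p(1-p) x n/2. The expected numerator of the estimate is p(1-p) x (n-K)/2. The ratio is 1 - K/n.

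| K | variance ratio | SE ratio | true size of the 10% test |
|---|---|---|---|
| 8 | 1 - 8/40 = 0.800 | 0.894 | 2(1 - Phi(1.645 x 0.894)) = 14.1% |
| 7 | 0.825 | 0.908 | 13.5% |
| 6 | 0.850 | 0.922 | 12.9% |

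For K = 8 a 95% interval covers 1 - 2(1 - Phi(1.96 x 0.894)) = 92.0%.

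**Simulation under the null.** Stratified blocks of 8, equal and unequal strata, 12,000-30,000 trials per complete-data scenario. The stratum mixes are assumed, because the documents give none. The null rates for F-VASI 75 and F-VASI 50 follow from the plan's placebo assumption if the change is normal: Phi(-75/54.8) = 8.6% and Phi(-50/54.8) = 18.1%.

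| Scenario | Rejection with large-stratum SE |
|---|---|
| 8.6% (F-VASI 75) | 14.5-15.1% |
| 18.1% (F-VASI 50) | 13.9-15.2% |
| common rates 10-50% | 13.5-15.5% |
| rates 5-40% across strata | 14.7-16.1% |
| Rubin pooling, 3-10% of values imputed | 13.5-14.9% |
| common rate 5% | 11.7-14.0% |
| common rate 3% | 9.1-10.5% |

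Simulated coverage of the 95% interval was 91-92%.

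**Comparators on the same simulated data, common rates of 8.6% or more.** The CMH chi-square rejects 9.6-10.8%. The same risk difference with the Sato (sparse-stratum) variance rejects 10.5-12.0%, with coverage of about 94-95%. The excess therefore comes mainly from the variance formula, not from the imputation or from the stratified estimator.

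**The case against.** The strongest objection is that the decisive fact is not in the documents. They name a procedure and a method but print no variance. If the software used a sparse-stratum form, rejection would be 10.5-12.0% and little would be wrong. This stands, and the size of the problem is conditional for that reason. It does not remove the point: the SAP leaves the variance behind a p-value unstated, and the p-value on this route is not the CMH p-value.

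A reader might infer more than the documents support, in four ways.

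- **That any imputed value triggers the problem.** SAP 9.1 sends the analysis to Appendix E only when the 30 datasets are not all identical. An imputed value that leaves the response status the same in every dataset changes nothing.
- **That the excess is a fixed 14-15%.** It shrinks with fewer informative strata and at low response rates. At 3% the test rejects about 10%, though CMH itself rejects only 6.6-7.7% there. The documents give no stratum prevalences and no null rate for T-VASI 50.
- **That the interval is computed differently on the two routes.** SAP 9.1 names no variance for the unpooled interval either, so only the change of p-value is shown.
- **That the Wald test should replace CMH everywhere.** CMH holds its level and is the test named in Protocol 7.4. Replacing it where nothing is pooled would slightly worsen error control.

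It is also fair that the code is only a sample with steps left out. As printed, the responder count would be missing rather than zero in a cell without responders; the calculation above assumes zero. Finally, these are secondary and additional endpoints in a Phase 2 study without multiplicity control. That limits the consequence, but SAP 13.0 still tests each endpoint at 0.1, and waiving familywise control does not justify a miscalibrated single test or intervals that under-cover.

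**Conclusion.** The point holds in conditional form. When the imputed datasets differ, the responder comparison moves from the CMH chi-square to a Rubin-pooled Wald test; that much can be read from the SAP. If PROC STDRATE uses the large-stratum variance, the standard error is about 10% too small. The nominal 10% test then rejects about 13-15% for common response rates of about 8% or more and 6-8 informative strata, somewhat more in the runs where rates differed between strata. Intervals labelled 95% cover about 91-92%. The result rests on 40 per arm, near-balanced arms within strata and that variance form. The MMRM and MCP-Mod analyses of the primary endpoint, and the sample size, are untouched. The change should be made: it is inexpensive, and following the named code would, under this assumption, give p-values and intervals that are too favourable.

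**What to change.** 1. In SAP Appendix E 2.5.1, state that each completed dataset yields the Mantel-Haenszel common risk difference with the Sato variance, and give the formula so that the result does not depend on a software default. With x1h and x0h responders, N_h = n1h + n0h, w_h as above and d the common risk difference: variance = (d x sum of P_h + sum of Q_h)/(sum of w_h)^2, where P_h = [n1h^2 x0h - n0h^2 x1h + n1h n0h (n0h - n1h)/2]/N_h^2 and Q_h = [x1h(n0h - x0h) + x0h(n1h - x1h)]/(2N_h).
2. Change the PROC STDRATE step in Appendix E 3.0 to match, set empty responder counts to zero, and pool this estimate and standard error in PROC MIANALYZE.
3. In SAP 9.1, use the same variance for the risk-difference interval when nothing is pooled, and keep the CMH chi-square p-value there.
4. Say openly that the pooled p-value is a Wald p-value.

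The cost is some SAP wording and one code step, with no new data. Standard errors for responder endpoints rise by roughly a tenth (for example 0.982/0.888 = 1.11 with equal strata at an 8.6% rate), so intervals widen and p-values become slightly less favourable. Some excess remains on the pooled route, where rejection is about 10.5-12%.
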